#### 6.3 Stopping Rules

The safety stopping rules will be applied to terminate a specific study cohort if more than one of the first three participants in the cohort suffers DLT which includes any SAE considered at least possibly related during the initial 7-day sequential DLT run-in (1+1+1); or at any time thereafter, if more than two participants in the cohort experience DLT (1+1+1, +6).

For the day-30 "boost" vaccination, the same 7-day sequential DLT run-in design (1+1+1, +6), and the same safety stopping rules apply.

Study enrollment and dosing will be halted if the following safety events are observed with the vaccination or the electroporation (EP) administration:

- 20% or more of subjects across all cohorts (7 or more subjects) experience the same or similar Grade 3 or higher adverse events assessed as at least possibly related to study treatment.
- Any death or SAE assessed as at least possibly related to study treatment.
- Any newly diagnosed pIMMC assessed as at least possibly related to study treatment.
- Any incidental or incorrect voltage or pulse delivery outside the specifications outlined in the User Manual

In the event study halting rules are triggered, the study's safety committee will review all available safety information, and determine whether enrollment and dosing are reasonably safe to continue for either or both vaccine formulations. The safety committee is comprised of three physicians with expertise in immunology who are not investigators on the study: [name], [name], and [name]. The committee's review and determination will be documented and submitted to the IRB and FDA.

# 6.4 Dose Delays

Treatment delay will be allowed for subjects with fever or other signs of an active infection on the day of planned vaccine administration, to include any evidence of infection upon evaluation of the administration sites. Treatment delay should continue until > 48 hours resolution of fever or other signs of active infection. In the event a subject reports symptoms consistent with COVID-19 or known exposure in the interval between 1st and 2nd vaccination, treatment delay is indicated until repeat COVID-19 qPCR is confirmed as negative, before proceeding with study treatment.

# 6.5 Subject Discontinuation & Replacement

In the event of a positive COVID-19 qPCR test result during the interval between 1st and 2nd vaccination, subject will discontinue study treatment and may be replaced. In the event of treatment delay exceeding 21 days, and absent DLT, subject will discontinue study treatment and may be replaced. In the event of a confirmed positive serum or urine pregnancy test, between 1st and 2nd vaccination, subject will discontinue study treatment and may be replaced. And otherwise, subjects who enroll in the study, and do not complete study treatment for reasons other than DLT, may be replaced.

Discontinuation for the following reasons does not allow for subject replacement: an SAE assessed as definitely/probably related to the investigational product; any Grade 3 or higher unsolicited AE, assessed as definitely/probably related to the investigational product; a new medical condition that would qualify for study exclusion; suspicion or diagnosis of pIMMC, as per section 6.1.

# 7. STUDY CALENDAR

Schedule of Events	Screen Day -9 to 1	Day 1	Day 2,3	Day 15	Day 30	Day 31,32	Day 45	Day 60	Day 90
Window (days)				+/-1	+/-1	+/-1	+/-1	+/-2	+/-2
Informed consent	Х								
Medical history, EKG 	Х								
Microbiome specimens 	Х								
NGS whole genome 	Х								
HIV, HBV, HCV serology 	Х								
Physical exam	Х				Х				Х
COVID-19 qPCR & serology 	Х				X 			Х	X 
CMP, CPK, CBC w/ diff	Х	Х	Х	Х	Х	Х	Х	Х	Х
UA and sediment	Х	Х	Х	Х	Х	Х	Х	Х	Х
Immune parameters 		Х	Х	Х	Х	Х	Х	Х	Х
b-HCG⁴		Х			Х				
Vital signs⁵		Х		Х	Х		Х		
CORVax  ( intradermal )		х			х				
pIL-12  ( intradermal )		Cohorts 1B, 2B			Cohorts 1B, 2B				
Adverse events 		Х		Х	MAAEs 		Х	MAAEs 	MAAEs 
Concomitant medications9	Х	Х	Х	Х	Х	Х	Х	Х	Х

1. Electrocardiograms (EKG) to include: heart rate (beats/min), PR interval (ms), QRS interval (ms), RR interval (ms), QT interval (ms), QTcB interval (ms), QTcF interval (ms), sinus rhythm (yes/no), and overall evaluation (normal/abnormal).

2. Refer to Lab Manual; microbiome specimens may be collected at any time up until start of study treatment. Refer to Lab Manual; 50mL whole blood in heparinized tubes (green top) and 5mL serum in SST tube; always collect pre-treatment on relevant study days; collect double baseline set on Day 1 of study.

- COVID-19 testing should be repeated at any time prior to 2nd vaccination if report of symptoms consistent with COVID-19 or known exposure. This will be performed using the Roche cobas® SARS-CoV-2 qPCR nasal swab and DiaSorin LIAISON® SARS-CoV-2 S1/S2 IgG serology platforms, (or updated institutional standard, at time of testing).
- 4. Serum or urine b-HCG (for WOCBP only) confirmed negative result on the day of vaccine administration.
- 5. Height at initial visit only; other vital signs at every indicated time point.
- 6. Refer to Procedure Manual for detailed administration instructions; monitor participants 1 hour post-treatment with vital signs q30 minutes x2, starting 10-15 minutes post vaccination; vitals review by study investigator required prior to release from clinic.
- 7. Adverse events/toxicity daily query by use of diary or RN/CRC phone call for seven days following each vaccination, including but not limited to injection site pain, redness, swelling, fatigue, headache, nausea, vomiting, diarrhea, myalgia, arthralgia, rash, new pain, dyspnea and temperature (see Appendix 1: Toxicity Grading). Subjects utilizing the diary for AE collection will be called on Day 7 by RN/CRC to review diary entries. On days 1, 15, 30, 45 where vital signs are indicated, AE assessment should be conducted in person by RN, or other PI designee.
- 8. Monitor for MAAEs at months 1, 2, 3, 6, 12 and 18 with contact by research RN or research associate for potentially immunemediated medical conditions (see Appendix 2: MAAEs/pIMMCs); repeat COVID-19 qPCR and antibody testing to be performed at any time during the 18 months safety monitoring in the event of potential exposure to SARS-CoV-2 (i.e., close contact tests positive for SARSCoV-2) or symptoms of SARS-CoV-2 infection, with full immunodynamic profiling (section 9) to be performed at the same time. In addition, voluntary extended immune monitoring under longitudinal research specimen protocol, will be offered to all study subjects at day 90.
- 9. Concomitant medications (including those administered prophylactically) will be collected from 30 days prior to Day 1 through Day 90. In addition, all medications associated with SAEs, MAAEs (including pIMMCs) will be collected through 18 months.

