# 1. RATIONALE

DNA vaccines have been widely explored and remain a promising immunotherapeutic strategy suitable for infectious diseases. DNA vaccines could represent an affordable, safe and effective alternative to conventional vaccines. Plasmid DNA-based vaccines are considerably faster and easier to manufacture than most other vaccine platforms. Further, DNA-encodable prophylactic vaccines with electroporation represent a safe and effective approach to initiate both humoral and cellular immunity in healthy volunteers directed at a variety of infectious diseases, including coronavirus.

The choice of immunogen for a DNA-encodable coronaviral vaccine is critical for not only the magnitude but also quality of immune response. The coronavirus spike (S) protein is composed of two subunits; the S1 subunit contains a receptor-binding domain that engages with the host cell receptor angiotensin-converting enzyme 2 (ACE2) and the S2 subunit allows viral-cell membrane fusion. Collectively, the S protein has been shown to induce long-term and potent neutralizing antibodies and/or protective immunity in various preclinical severe acute respiratory syndrome (SARS)-CoV studies and in both preclinical and clinical studies in Middle East Respiratory Syndrome (MERS)-CoV studies. These previous vaccine studies, which were based on the spike protein from different strains of coronavirus, provide an immunological framework for this vaccine concept.

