# 2. BACKGROUND

Coronaviruses, which can infect and cause disease in both mammals and birds, typically lead to mild respiratory infections such as the common cold. However, although rare, coronavirus strains such as Severe Acute Respiratory Syndrome (SARS-CoV) and Middle East Respiratory Syndrome (MERS-CoV) can be lethal.

On December 31, 2019, a novel strain of coronavirus, coined SARS-CoV-2 by the World Health Organization (illness from SARS-CoV-2 is COVID-19), was discovered after tracing the origins of a pneumonia outbreak in Wuhan, China. SARS-CoV-2 identifies as a novel strain of betacoronavirus that is capable of person-to-person spread. Previous international emergency betacoronavirus outbreaks include both the genetically similar SARS-CoV (Severe Acute Respiratory Syndrome) and MERS-CoV (Middle East Respiratory Syndrome).

The World Health Organization has determined the COVID-19 outbreak to be a global pandemic. To combat the rapid spread of the virus, governments across the world, including the United States, have taken steps to limit spread, including travel restrictions, sheltering in place, and quarantines. Because coronaviruses typically present with symptoms mirroring the common cold, there has historically been a low interest in developing an antiviral. However, with the progression of the current pandemic, the need to develop vaccines that can help contain these viruses has become clear.

As further described below, Drs. [name], [name], and colleagues have worked with researchers at OncoSec Medical Incorporated (OncoSec) to develop a novel vaccine approach for COVID-19. The plan is to employ OncoSec's proprietary gene delivery system, using established electroporation technology to deliver a plasmid-based DNA vaccine encoding the SARS-CoV-2 spike (S) glycoprotein together with a plasmid encoding IL-12p70.

Here, we describe both a novel DNA-encodable vaccine approach which includes the use of the IGEA CLINIPORATOR® - Model EPS02 ("CLINIPORATOR") generator, which provides a favorable transfection profile. The CLINIPORATOR® generator achieves its high transfection efficiency by using a lower voltage with longer duration pulses, which, based on preclinical evaluation of OncoSec's generator (with identical electroporation parameters), have resulted in improved expression of the electroporated genes.

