# Rationale for vaccine route of administration and dose

The rationale for administering plasmid encoding the SARS-CoV-2 (S) protein to the dermis includes several points. We hypothesize that dermal expression of both IL-12 and SARS-CoV-2 (S) protein will result in limited expression within the nearby dermis, leading to antigen presentation in the draining lymph node that, secondary to the influence of IL-12, will result in the priming of an anti-viral immune response that is polarized to a type 1 immunity. By comparing the immune response of subjects receiving SARS-CoV-2 (S) alone with those receiving SARS-CoV-2 (S) plus IL-12, we will be able to test our hypothesis that inclusion of IL-12 will augment the magnitude and breadth of the T and B cell anti-viral response. The rationale for the dose of 0.8 mg into the dermis is based on the relatively small differences in the antibody response of subjects receiving electroporation of plasmid vaccines. Further, a current vaccine study for SARS-CoV-2 is electroporating 1 or 2 mg of plasmid into the dermis. In this study subjects will receive either 0.8 mg of spike protein alone or 0.8 mg of spike protein combined with 0.8 mg of IL-12 plasmid.

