# 9.2 Neutralization assay

Antibody neutralization of the SARS-CoV-2 will be assessed using a pseudotyped lentivirus expressing the SARS-CoV-2 (S) protein and luciferase. Readout will be the ability of sera from vaccinated candidates to prevent infection of susceptible target cells. Alternatively, a surrogate viral neutralization test, reporting ability of sera to block hACE2R binding to spike will be performed.

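### After dose 1 a positive S1/S2 IgG cannot separate infection from vaccination, so a silent infection that clears between swabs could be read as vaccine response

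*Combined protocol and SAP*

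**What the plan says.** Section 2 describes the product as "a plasmid-based DNA vaccine encoding the SARS-CoV-2 spike (S) glycoprotein together with a plasmid encoding IL-12p70". On the antigen, section 1 states: "The coronavirus spike (S) protein is composed of two subunits; the S1 subunit contains a receptor-binding domain"; the other subunit is S2.

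Footnote 3 of the study calendar (section 7) names the COVID-19 tests: a nasal-swab qPCR and "SARS-CoV-2 S1/S2 IgG serology platforms, (or updated institutional standard, at time of testing". The calendar marks the pair at screening and again at Days 30, 60 and 90. Footnote 3 asks for a repeat before dose 2 if there are symptoms or a known exposure. Footnote 8 carries this further: "repeat COVID-19 qPCR and antibody testing to be performed at any time during the 18 months safety monitoring", again triggered by possible exposure or symptoms.

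The rules that act on infection between the doses use the swab alone. Section 6.4 says that "treatment delay is indicated until repeat COVID-19 qPCR is confirmed as negative". The rule in section 6.5 begins "In the event of a positive COVID-19 qPCR test result during the interval between" the two vaccinations, and it ends study treatment in that case.

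The immune readouts look at spike. Section 9.2 uses a "pseudotyped lentivirus expressing the SARS-CoV-2 (S) protein and luciferase", or alternatively a test of whether serum blocks spike from binding its receptor. Section 9.4 measures spike-specific T cells. Section 9.5 targets antibody to spike, by bead array or ELISA. Section 2, on route and dose, gives the purpose: "By comparing the immune response of subjects receiving SARS-CoV-2 (S) alone with those receiving SARS-CoV-2 (S) plus IL-12", the plan expects to test whether IL-12 augments the response.

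**The concern.** The named serology is sound for screening, before any dose. After Day 1 it measures antibody to the antigen that the vaccine is meant to raise, so a vaccine that works should turn it positive. The scheduled post-dose serology therefore cannot confirm infection, and within the plan as written that task falls to qPCR.

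A swab detects infection only while the virus is present. A participant who is infected without symptoms, reports no exposure and clears the virus between two scheduled swabs would be qPCR-negative at both. Any resulting rise in spike antibody or spike-specific T cells would then enter the section 9 readouts as vaccine response.

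A related gap does not depend on missed infections. Where an infection is detected, no text says how that participant's later immune samples are to be summarised.

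At stake is how cleanly the exploratory comparison of CORVax alone with CORVax plus pIL-12 can be read, with 9 participants per cohort and 18 per formulation.

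**Working it through.** The plan states no infection-detection figure to reproduce. The check is first logical, then a rough scale.

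**What each post-dose result can mean**

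| Finding after dose 1 | Reading |
|---|---|
| qPCR positive | current infection |
| S1/S2 IgG positive, qPCR negative | vaccination, past infection, or both |
| S1/S2 IgG negative | argues against an earlier infection |
| Spike rise between Days 60 and 90, last dose at Day 30 | out of phase with dosing, so a clue to infection |
| Antibody to a non-spike viral protein, new since Day 1 | points to infection; not specified in the plan |

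**Swab spacing (section 7).** Nominal gaps are about 30 days. With the visit windows, the longest are 31 − (−9) = 40 days (screening to Day 30), 62 − 29 = 33 days (Day 30 to 60) and 92 − 58 = 34 days (Day 60 to 90).

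**Share of infections that fall between swabs.** Assume onset uniform over Days 1 to 90 (89 days), routine swabs at Days 30, 60 and 90, and swab positivity lasting D days. Missed share = 1 − 3D/89.
- D = 10: 0.663
- D = 14: 0.528 (onset on Days 1–16, 30–46 or 60–76, which is 15 + 16 + 16 = 47 of 89 days)
- D = 21: 0.292

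**Chance of at least one such infection among 36.** Let p be the 90-day attack rate and a the asymptomatic share. Then q = p × a × missed share, and the chance is 1 − (1 − q)^36. None of p, a or D is in the documents. All symptomatic infections are taken as caught.

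| p | 36q (a = 0.5, D = 14) | Chance of at least one | Range, from (a = 0.3, D = 21) to (a = 0.7, D = 10) |
|---|---|---|---|
| 1% | 0.10 | 9% | 3–15% |
| 2% | 0.19 | 17% | 6–29% |
| 5% | 0.48 | 38% | 15–57% |

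These are upper bounds for those inputs, because q gives no credit for the exposure-triggered swabs that footnotes 3 and 8 require. Exclusion 4.2.21, which keeps out people at high exposure risk, argues for the lower values of p. The bound takes all three post-dose swabs as routine. If the footnoted Day 30 and Day 90 marks were only conditional, the missed share at D = 14 would be about 84%.

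**Weight of one participant.** 1/9 = 11.1 percentage points of a cohort and 1/18 = 5.6 of a formulation. That is a maximum, reached only if the participant would not otherwise have responded. Section 11.1 defines no immune response rate, so this is scale and not a planned statistic.

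**Could a non-spike antibody catch these infections?** At D = 14, a missed infection is 30 − 16 = 14 to 30 − 1 = 29 days old at the Day 30 draw. It is 60 − 46 = 14 to 60 − 30 = 30 days old at Day 60, and likewise 14 to 30 at Day 90. The test covers these windows if antibody appears within 14 days (assumed).

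**False positives.** There would be 36 × 3 = 108 post-dose tests. At an assumed specificity of 99% to 99.8%, 108 × 0.01 = 1.1 to 108 × 0.002 = 0.2 first-pass false positives are expected.

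**The case against.** The strongest reply is that little is at risk. Immunogenicity is exploratory, and section 9.7 itself acknowledges the small numbers. Section 11.1 plans only baseline and safety summaries, so any response-rate shift applies to a summary that the plan has not defined. Every infection rate above is assumed, and the exposure-triggered swabs would catch some of the infections counted as missed. All of this stands. It is why the percentages are bounds on assumed inputs and the point is a minor one.

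Second, the serology is not blank after dosing. A negative result is informative. A late spike rise could expose infections from the Day 60–76 window, 16 of the 47 missed days. That stands too, but it does not help for onset on Days 1–16 or 30–46, when a rise after a dose is expected anyway.

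Third, the plan leaves openings. Footnote 3 allows a later local standard, the section 9.5 bead arrays carry unnamed SARS-CoV-2 proteins, the Lab Manual is not available here, and stored samples could be tested later. These are openings and not commitments. Another spike assay would satisfy footnote 3, ELISA may replace the array, and no infection rule is attached to either. Stored samples keep the remedy available, but a definition fixed before the immune data are seen is worth more than one added afterwards.

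Fourth, the remedy could mislabel people. First-pass false positives (0.2 to 1.1) are of the same order as the expected missed infections (0.10 to 0.48). With perfect sensitivity, an initial positive would be a true missed infection in 0.10/(0.10 + 1.08) = 8% to 0.48/(0.48 + 0.22) = 69% of cases. Rerunning the same serum on the same assay may simply repeat a cross-reaction. This is a fair criticism, and it shapes the confirmation rule in the fix.

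**Conclusion.** The point holds for the tests as named. After dose 1, a positive S1/S2 IgG cannot separate infection from vaccination, and the plan commits to no other marker that could. An asymptomatic infection with no reported exposure that clears between swabs could therefore be read as vaccine response in sections 9.2, 9.4 and 9.5. The size is small: at most 1/9 of a cohort or 1/18 of a formulation per such participant, with a probability that the documents do not determine.

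Three stronger readings are tempting, and the documents do not support them:
- **That vaccinated participants would be wrongly held or withdrawn as infected.** Sections 6.4 and 6.5 act on qPCR, not serology.
- **That the comparison is tilted toward IL-12.** Section 5 randomises 1:1 to A or B within age group, so a missed infection adds noise and not a systematic advantage to either formulation.
- **That the safety conclusions are affected.** The primary safety summaries in sections 10.4 and 11.1 rest on adverse events and do not use the spike readouts.

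This is worth considering because it is cheap to put right. It is not a defect in the primary objective.

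**What to change.** 1. **Footnote 3 and section 9.5.** Name an antibody to a SARS-CoV-2 protein that CORVax does not encode, for example nucleocapsid. Run it on the serum already drawn at Days 1, 30, 60 and 90 and at testing triggered under footnote 8. The month 6, 12 and 18 contacts need no added test. If the section 9.5 array already carries such a protein, naming it and its use is enough.
2. **Definition of infection after dose 1.** A positive qPCR, or non-spike antibody that is new since Day 1 and confirmed on a second sample or a different assay where available. Day 90 is the last scheduled draw, so a first positive there will usually need the different assay.
3. **S1/S2 IgG.** Keep it for screening and as a measure of vaccine response, not as evidence of infection after dosing.
4. **Section 9 summaries.** Show immune results with and without samples taken after an infected participant's last infection-negative visit. This discards nothing and also covers infections detected by qPCR.

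Cost: 36 × 4 = 144 assays on existing serum, plus the triggered ones, where blood is already taken for full profiling. No new visits or draws are needed. The downside is a few possible false positives, which the confirmation rule reduces and the two-way summary makes visible.

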### **10.4 Continuing Review and Final Reports**

An annual progress report (continuing review) will be submitted to the IRB for the duration of the study. A final report to the IRB will be submitted at the summation of the study.

All IND annual reports, clinical trial reports, and clinical trial report addenda submitted to the FDA will include tabulated summaries of available adverse event data for potentially immune-mediated medical conditions reported during the trial, categorized by MedDRA term. These summaries will include any conditions reported during the trial that match the terms listed in Appendix 2, as well as any other potentially immune-mediated medical conditions (pIMMCs) reported during the trial that do not appear on the list in Appendix 2. For each adverse event included in the summaries, a case narrative will be provided, along with an assessment of the seriousness of the event and causal relationship to study vaccine, as required by 21 CFR 312.32.

Collection of MAAE data beyond 6 months after the last study vaccination will not delay submission of clinical trial reports and initiation of subsequent clinical trials, and final analyses of MAAEs may be submitted in clinical trial report addenda.

The safety analysis in the final clinical study report will include the number and proportion of subjects in each cohort reporting 1) each solicited AE of any grade through seven days following any dose and each dose, 2) each solicited AE grade 3 and greater within seven days following any dose and each dose, 3) unsolicited AEs of any grade reported at a minimum through 28 days following dose 2, 4) unsolicited AEs grade 3 and greater reported at a minimum through 28 days following dose 2, 6) SAEs, MAAEs, and pIMMCs reported through one year following dose 2. In addition, it will include the number and proportion of subjects in each cohort of each category of AE that the investigator assessed as related.

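### General adverse event queries are clearly scheduled only to Day 45, short of the 28 days after dose 2 that Section 10.4 commits to report; vital signs also stop at Day 45 against a 90-day primary outcome

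*Combined protocol and SAP*

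**What the plan says.** **Collection (Section 7, Study Calendar).** The AE row is marked X at Days 1, 15 and 45, and MAAEs at Days 30, 60 and 90. Footnote 7 sets a "daily query by use of diary or RN/CRC phone call for seven days following each vaccination". It adds: "On days 1, 15, 30, 45 where vital signs are indicated, AE assessment should be conducted in person by RN". Footnote 8 describes the MAAE contacts at months 1, 2, 3, 6, 12 and 18 as made "with contact by research RN or research associate for potentially immunemediated medical conditions". Footnote 9 uses the term more broadly: "all medications associated with SAEs, MAAEs (including pIMMCs) will be collected through 18 months".

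**Reporting (Section 10.4).** Item 3 of the final safety analysis is "unsolicited AEs of any grade reported at a minimum through 28 days following dose 2". Item 4 is "unsolicited AEs grade 3 and greater reported at a minimum through 28 days following dose 2". A separate item 6 is "SAEs, MAAEs, and pIMMCs reported through one year following dose 2".

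**Outcomes (Section 3).** The measures under the primary objective include 90-day monitoring of physical examination, vital signs and a durable pain score. The vital-signs row is marked at Days 1, 15, 30 and 45 only, and footnote 5 ties vital signs to the marked time points. Section 8.6 schedules pain assessment on Days 1 and 30. Footnote 7 adds daily queries for seven days after each dose, "including but not limited to injection site pain, redness, swelling, fatigue, headache, nausea, vomiting, diarrhea, myalgia, arthralgia, rash, new pain".

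**The concern.** Safety is the only primary objective, and Section 11.1 summarises it as the percentage of participants with AEs. That percentage depends on participants being asked. Followed literally, the calendar stops asking a general AE question before the end of the period that Section 10.4 promises to report.

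The loss would fall mainly on item 3, unsolicited AEs of any grade. Grade 3 or higher events (item 4) are more likely to be medically attended or to appear in the Day 60 laboratory results. Solicited reactions, SAEs and immune-mediated conditions have their own follow-up. What is exposed is the symptomatic event for which nobody sought care. A low percentage for that period could mean few events or few questions, and the report could not tell the two apart.

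Vital signs raise the same problem in simpler form: a component of the primary outcome has no scheduled measurement in the second half of its stated period.

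**Working it through.** The plan gives no figure of its own to reproduce. The check is day arithmetic on the calendar. A day counts as covered if a later scheduled general AE assessment can look back over it.

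**Inputs**
- Dose 2: Day 30, window ±1 (Section 7).
- Last clearly scheduled general AE assessment: Day 45, window ±1 (Section 7, AE row and footnote 7).
- Next visit: Day 60, window ±2, marked MAAEs (Section 7).
- Required period: at least 28 days after dose 2 (Section 10.4).
- Dose 2 delay allowed: up to 21 days (Section 6.5).
- Cohort size: 9; analysis set is all treated participants (Section 11.1).

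**Nominal gap**
- End of required period: 30 + 28 = Day 58.
- Covered: 45 − 30 = 15 days.
- Not covered: 58 − 45 = 13 days; 13/28 = 46%.

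**With visit windows.** The plan does not say whether windows run from Day 1 or from dose 2, so both are shown.

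| Windows counted from | Days covered | Days not covered | Share of 28 | Day 60 visit, days after dose 2 |
|---|---|---|---|---|
| Dose 2 | 15 ± 1 = 14 to 16 | 14 to 12 | 50% to 43% | 30 ± 2 = 28 to 32 |
| Day 1 | 44 − 31 = 13 to 46 − 29 = 17 | 15 to 11 | 54% to 39% | 58 − 31 = 27 to 62 − 29 = 33 |

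**With a delayed dose 2.** The calendar does not say whether later visits move. If they stay on the Day 1 clock (an assumption), a 21-day delay puts dose 2 on Day 51 and ends the required period on Day 51 + 28 = Day 79. The Day 45 assessment then comes before dose 2, and only the seven-day query is left. The Day 60 visit would fall 60 − 51 = 9 days after dose 2. If visits move with dose 2, the dose 2 row of the table applies.

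**Does the MAAE label close the gap?** Three readings:
1. Narrow (footnote 8): immune-mediated conditions only. The gap stands.
2. Broad (footnote 9): all medically attended events. Events without medical attendance are still outside its scope, and Section 10.4 reports MAAEs (item 6) apart from unsolicited AEs (items 3 and 4).
3. An addition to a general assessment. Day 30 points this way: it carries the label, yet footnote 7 requires an AE assessment that day. But footnote 7 names Day 30 and does not name Day 60.

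**Effect on a reported percentage (illustration only; the plan gives no event frequency).** If one participant's only unsolicited AE falls in the gap and is missed, the cohort figure drops by 1/9 = 11.1 points, or 1/10 = 10.0 points if one treated participant has been replaced.

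**Vital signs.** Last scheduled Day 45; 90 − 45 = 45 days with none. Physical examination (Day 90) and safety laboratory tests (Days 60 and 90) do continue.

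**The case against.** The best defence is that footnote 7 governs the mode of assessment on four days (in person) and does not say that AE assessment ends there. The Day 30 cell shows that the MAAE label need not displace a general assessment, and no passage gives the questions asked at an MAAE contact. Participants attend at Day 60 anyway for blood tests, urinalysis, COVID-19 testing and medication review, and nothing tells staff to stop recording AEs after Day 45. On this view the issue is one ambiguity at one visit. The percentages measure time between visits, not lost data: if Day 60 looks back, the gap disappears. The 1/9 illustration is true of any missed event in a cohort of nine. The 90-day phrase in Section 3 covers a group of measures and need not promise each one throughout.

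Much of this limits the size of the problem. The day counts are not a loss estimate, the illustration says nothing about likelihood, and the pain point is largely wording. It does not supply the missing query. No passage schedules a general AE question after Day 45. Laboratory tests and medication review do not detect an untreated symptom, and the weekly review in Section 10.7 is not a participant assessment. The vital-signs mismatch also stands: vital signs have their own grades in Appendix 1 and their own calendar row, which ends at Day 45.

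**Conclusion.** The concern holds and should be fixed. For a Day 30 boost, 13 of the 28 days after dose 2 (46%) lie beyond the last clearly scheduled general AE query. The range is 12 to 14 days if visit windows run from dose 2 and 11 to 15 if they run from Day 1. These figures assume an on-time dose 2 and that Day 60 is not a general AE assessment, which is how the calendar and footnotes 7 and 8 most naturally read. A delayed dose 2 could widen the gap if later visits do not move with it. How many events would be missed cannot be estimated from the documents; the exposure is mainly lower-grade events without medical attendance.

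Vital signs have no scheduled measurement for 45 of the 90 days that Section 3 names. The 90-day pain wording does not match Section 8.6 and footnote 7 either; that is the least consequential part.

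**What to change.** 1. In the Section 7 calendar, mark the Day 30 and Day 60 AE cells as general AE assessment plus MAAEs.
2. Define MAAE once, so that footnotes 8 and 9 and item 6 of Section 10.4 use it alike.
3. State that the Day 60 query looks back to the Day 45 assessment and takes place at least 28 days after the actual dose 2 date.
4. State whether visit windows run from Day 1 or from dose 2. From dose 2, an on-window Day 60 visit always falls 28 to 32 days after it. From Day 1, it can fall at 27 days, one short, even with an on-time boost.
5. Either add vital signs at the existing Day 60 and Day 90 visits, or restate that outcome in Section 3 as through Day 45.
6. Reconcile the 90-day pain wording in Section 3 with Section 8.6 and footnote 7.

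The cost is small: one open AE question, and vital signs if chosen, at visits already held for blood draws, plus wording changes in Sections 3, 7 and 8.6. Sample size and treatment are unaffected.
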